9.4.3. Reporting Requirements for Participating Sites

The research team at each participating site is required to promptly notify the Washington University PI and research coordinator of all reportable events within **1 working day** of the occurrence of the event or notification of the participating site's PI of the event. This notification may take place via email if there is not yet enough information for a formal written report. A formal written report must be sent to the Washington University PI and research coordinator within **10 working days** of the occurrence of the event or notification of the secondary site's PI of the event. The death of a research participant that qualifies as a reportable event should be reported within **1 working day** of the occurrence of the event or notification of the participating site's PI of the event.

The research team at a participating site is responsible for following its site's guidelines for reporting applicable events to its site's IRB according to its own institutional guidelines. Since sites will be relying on Washington University's IRB, any reportable event will also be submitted to Washington University's IRB for review.

9.4.4. Reporting to Participating Sites

The Washington University PI (or designee) will notify the research team at each participating site of all reportable events that have occurred at other sites within **10 working days** of the occurrence of the event or notification of the PI of the event. This includes events that take place both at Washington University and at other participating sites, if applicable.

9.4.5. Reporting to MyoCardial Solutions

The following adverse events will be reported to MyoCardial Solutions within **10 working days** of the occurrence of the event or notification of the PI of the event at either Washington University or any participating site unless the event occurs in a death, in which case it will be reported within **1 working day**:

Term	Description
Device Related Adverse Event (DRAE)	An adverse event will be considered to be related to the device if it results from the use or presence of the MRI Scanner, or the performance of any component of the MRI Scanner.
Unanticipated Adverse Device Effect (UADE)	A device or procedure related adverse effect will be considered unanticipated if it is not identified in the MRI Scanner or SENC MyoStrain® Testing Software operator manuals or instructions for use.

9.4.6. Timeframe for Reporting Required Events

Adverse events will be tracked from time of consent to the last study visit. For the purposes of this protocol, adverse events collected and documented on CRFs include adverse events occurring from the MRI scanner, SENC MyoStrain® Testing Software, or breach of confidentiality.

All incidences of noncompliance and protocol exceptions will be tracked from the time of IRB approval, at the coordinating center, or site initiation at the participating centers, until the close of the study.

For more information on adverse event definitions and classifications and reporting requirements, please visit: <https://www.hhs.gov/ohrp/regulations-and-policy/guidance/reviewing-unanticipated-problems/index.html>

10. DATA SAFETY AND MONITORING

10.1.1. Data Monitoring by MyoCardial Solutions

Monitoring of the research is the responsibility of the Principal Investigator at each participating site. The participating sites and Myocardial Solutions will meet on regular basis to discuss the progress of the research and the efficiency of the PROACT study.

10.1.2. Data Monitoring by Coordinating Sites

The data consist of information obtained from MyoCardial Solutions, Inc. MyoStrain® software. Data will be stored in two places: 1) a WUSTL REDCap database and 2) all original paper copies will be stored in a locked cabinet behind a locked door at each participating site. Moreover, only the Research Coordinator or designated study staff will have keys to the locked cabinet. Only the designated study staff will have access to any resources with identifying information in REDCap. An important REDCap feature to note is that the access to study data is limited to those assigned access (i.e. Key Study Personnel [KSP]).

Data and regulatory documents from all participating sites will be reviewed by the Washington University Quality Assurance and Safety Monitoring Committee (QASMC) every 6 months. For participating sites added on after study initiation, the first review for that site will take place during the next scheduled QASMC review, which may occur prior to 6 months after site initiation. Because all monitoring will take place remotely, uploads of source documentation, including consent forms with signatures, either to REDCap and/or WUSTL Box will be mandatory for participating sites. In addition, QASMC may request access to participating sites' electronic medical record, if the site's institution allows such access.

Data and regulatory document monitoring will also be conducted by the coordinating center's research coordinators and will consist of data checks, both electronic and manual. Every 6 months prior to QASMC review, data entered into the REDCap database will be reviewed for accuracy by designated study staff at the coordinating center. As with QASMC audits, for participating sites added on after study initiation, the first review for that site will take place during the next scheduled data review. Uploaded source documentation, including consent forms with signatures, by participating sites will also be reviewed for inconsistent data. If there are inconsistencies or missing values, queries will be issued to the participating sites and they will refer to the subject's records to correct the aberration. Participating sites are expected to enter data into REDCap within 14 business days of a study visit. Sites that appear to have significant delays between the time of enrollment/study visits and data entry will be contacted by the coordinating center. Participating sites are also expected to respond to any REDCap queries within 1 month of issuance. Sites that appear to have a significant amount of REDCap queries will be contacted by the coordinating center. At each interval, the coordinating center will note the number of participants accrued to date as well as the number of participants accrued for that 6 months interval.

All study personnel will receive training on protocol procedures and data collection from the coordinating center. Only experienced personnel will take part in this study. Additionally, designated study staff will randomly monitor the consenting process pertinent to this study to maintain study protocol compliance, as well as ensure the minimization of measurement or information bias imposed by study personnel.

10.1.3. Data Safety and Monitoring Committee

In compliance with the Washington University Institutional Data and Safety Monitoring Plan, the Principal Investigator will provide a Data and Safety Monitoring (DSM) report to the Washington University Quality Assurance and Safety Monitoring Committee (QASAMC) semi-annually beginning six months after accrual has opened (if at least 5 patients have been enrolled) or 1 year after accrual has opened (if fewer than 5 patients have been enrolled at the 6 month mark).

The Principal Investigator will review all patient data at least every 6 months, and provide a semi-annual report to QASMC. The report will include:

- HRPO protocol number, protocol title, Principal Investigator name, and research coordinator name
- Date of initial HRPO approval, date of most recent HRPO approval/revision of consent, date of HRPO expiration, date of most recent QA audit, study status, and phase of study
- History of study including summary of substantive amendments; summary of accrual suspensions including start/stop dates and reason; and summary of protocol exceptions, error, or breach of confidentiality including start/stop dates and reason
- Study-wide target accrual and study-wide actual accrual
- Protocol activation date
- Average rate of accrual observed in Year 1, Year 2, and subsequent years
- Expected accrual end date

- Objectives of protocol with supporting data and list of the number of participants who have met each objective
- Abstract submissions/publications
- Summary of any recent literature that may affect the safety or ethics of the study

11. STATISTICAL CONSIDERATIONS

The data of cardiac features measured will be stored in a WUSTL REDCap-supported database and transformed into a SAS, R, excel, and CSV dataset, so they can be analyzed by our team using SAS, R and PYTHON software packages.

At baseline and any other visit, the standard descriptive statistics will be used to summarize numeric variables, including the number of observed values, mean, standard deviation, median, minimum and maximum values. Summaries of categorical variables will include the number and percentage of observed values, at each level of the categorical variable. Baseline and demographic information will be summarized with standard descriptive statistics.

There will be more than 60 cardiac 3D features measured for each patient (subjects' n=102) resulting from use of MyoStrain SENC software, as shown in the schematic Figure 5. The results will be stratified based on the patient's segmental strain (longitudinal and circumferential) profile with -10% or -17% as the threshold to determine segmental dysfunction and the number of dysfunctional segments delineating patient risk. The patients will be selected at baseline for high cardiovascular risk, which will be important in cancer patients in responding to cardiotoxicity.

Patients will be separated by randomization into two groups. Those of whom the cardiac care will be served with prior knowledge of MyoStrain SENC data as measured in each visit, while the other half, with exception of 4 cardiac measures, they and their doctor will not have knowledge for the full cardiac features, but we will have access to these data also, only at the end of the study.

[figure not shown]

Figure 5: A schematic of measurements and statistical methods to be used for inferring for cardiotoxicity from results of baseline and also at 1, 3, 6, 12, 24 and 36 months' follow-up.

The longitudinal data will be compared for each individual with his/her baseline, to learn and guide each individual's care and to infer the level of cardiotoxicity. The same group's data will be analyzed with the intention in identifying what trends exist among those in the group of MyoStrain SENC software guided treatment. The full cardiac measures for the other group: the observational arm will be available to us at the end of the trial. At that time, we will analyze also the longitudinal cardiac 3D features for this group at the individual levels compared to baseline. In addition, we will analyze the longitudinal data to identify trends for each group, as well as we will compare trends of two groups toward cardiac response to chemotherapy and / or radiology. We will test the cardiotoxicity development i.e. myocardial dysfunction by comparing the efficacy of detecting cardiac dysfunction using standard assessments LVEF, LVESV and LVEDV in time against analyzing all cardiac features collected via MyoStrain (more than 60 of them, Figure 5). Multivariate regression and logistic regression will be used with "stepwise" option to identify significant predictors at standard and guided care features for predicting cardiotoxicity. Furthermore, we will use decision trees for identifying the

importance of MyoStrain cardiac features compared to cardiac toxicity risk prediction based on standard assessment of variables LVEF, LVESV, LVEDV, and LV Stroke Volume Index (LVSVi). Endpoints will be evaluated based on discrete variables of MyoStrain values versus standard assessments. Considering many patients will have a complex management of cardioactive medications as well as cancer treatment regimen, the classification of cardiotoxicity status will be based on a clinical committee to designate whether the patient experienced no cardiotoxicity, functional decline without cardiotoxicity, subclinical cardiotoxicity, or clinical cardiac dysfunction at each exam timepoint. The last analysis will help to identify also any indication for interactions among variables studied. We will implement Intention-To-Treat-analysis, where the analyses of the two groups will be based on the initial treatment assignment in the two randomized groups. If in the follow-up data-points may be missing, we will check if the missing data-points are random and if several covariates can help in imputation of missing. We plan to use MI procedure of SAS Institute for such imputations. The regression will be implemented via GLM, LOGISTIC and MIXED (for statistical analysis of repeated measures) procedures in SAS. For mixed models, a comparison of models will be done via likelihood ratio test and by using the Akaike Information Criterion (AIC) and Schwartz's Bayesian Criterion (SBC). Graphical presentations will be implemented in R via LMER of LME4 mixed modelling build in functions, and specialized software GGPlot2 in R. Decision (known also as partition) trees will be implemented with SAS-Data Mining software. We will use also PYTHON-scikit machine learning package for testing the performance of partition-trees via random forest. A random forest is a meta estimator that fits a number of decision tree classifiers on various sub-samples of the dataset and use averaging to improve the predictive accuracy and control overfitting.

Based on pilot data and utilizing only the moderate to high risk group (>2 segments of Myostrain determined segments >17%), the outcome expected would be 12.8 +/- 4.7 dysfunctional segments for the intervention group and 16.8 +/- 7.8 dysfunctional segments for the control group (and using average of 4.7 and 7.8 for the standard deviation for the overall outcome) at 6 months. This same parameter will be followed at the other time points, including 1 year, 2 years, and 3 years, but the primary endpoint will be at 6 months. With these calculations, 102 patients are required to have a 90% chance of detecting, as significant at the 5% level, a decrease in the primary outcome measure from 16.8 in the control group to 12.8 in the experimental group (number of dysfunctional segments (>17%)).

The sensitivity, specificity, and diagnostic accuracy of each reader to detect changes in myocardial function will be determined for quantitative SENC-CMR. Cutoff-values used to calculate sensitivity and specificity of the quantitative SENC parameters were determined using data previously published. The cutoff for the % of MyoStrain segments <= -17% (based on 37 left ventricular segments) in detecting subclinical cardiotoxicity in the PREFECT50 planned interim analysis was 68% and the cutoff for detecting clinical cardiac dysfunction was 49%; a cutoff of 80% differentiates normal cardiac function from patients experiencing functional decline. McNemar's test with continuity correction will be used to compare the diagnostic performance of each of the SENC-CMR cutoff parameters. Additionally, Receiver Operating Characteristic curves as well as Precision Recall curves will be generated to calculate and compare the area under the curves to determine the diagnostic performance of changes in strain parameters and standard assessments. Inter- and intra-observer variability will also be determined for each of the above parameters using intraclass correlation.

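### Stepwise selection of significant predictors from more than 60 MyoStrain features in 40 patients, with no validation stated, gives invalid p-values and, if scored on the same data, an inflated multi-feature fit

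*Combined protocol and SAP*

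**What the plan says.** Section 11 describes testing the detection of cardiac dysfunction by LVEF, LVESV and LVEDV "against analyzing all cardiac features collected via MyoStrain (more than 60 of them, Figure 5". The data are described as "more than 60 cardiac 3D features measured for each patient". The method follows directly: "Multivariate regression and logistic regression will be used with 'stepwise' option to identify significant predictors at standard and guided care features for predicting cardiotoxicity". LV stroke volume index joins the standard measures in the decision-tree comparison, so the standard set has three or four members.

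The outcome is a four-category status assigned by a clinical committee. The last two categories read "subclinical cardiotoxicity, or clinical cardiac dysfunction at each exam timepoint", so status belongs to an exam. Section 5.1 schedules six follow-up exams per patient.

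Section 5.7 (with 1.8 and 5.6) sets 40 evaluable patients. Section 11 still prints 102 for this analysis.

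Four other statements in Section 11 bear on the point:

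- On trees: "We will use also PYTHON-scikit machine learning package for testing the performance of partition-trees via random forest".
- On mixed models: "For mixed models, a comparison of models will be done via likelihood ratio test and by using the Akaike Information Criterion (AIC", together with Schwarz's criterion.
- On endpoints: "Endpoints will be evaluated based on discrete variables of MyoStrain values versus standard assessments".
- On cutoffs: "Cutoff-values used to calculate sensitivity and specificity of the quantitative SENC parameters were determined using data previously published".

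For the stepwise regressions, the visible text gives no entry or stay level, cross-validation, hold-out sample, bootstrap correction or penalty.

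**The concern.** There are two problems, and they differ in how firmly they follow from the text.

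(a) A p-value printed for a stepwise-selected term is computed as if that term had been named in advance. After a search over 60 or more candidates it no longer has its nominal meaning. This holds whether the two feature sets are fitted separately or pooled, and at 40 or 102 patients. The plan's stated product is a list of significant predictors, so the product itself is unsound.

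(b) If performance is read from the data used for selection, a search over 60 candidates finds more chance fit than a search over three or four. The plan does not say how the models are scored or whether the sets are fitted separately, so this part is conditional.

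The second primary objective (Sections 1.4 and 3) is to compare MyoStrain with standard cardiac imaging. A list of significant strain features, or a higher same-sample AUC, could be reported as support for that objective when it is neither.

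**Working it through.** **Sample size.** The plan gives no figure for the stepwise analysis. Its 102 comes from the 6-month segment comparison: difference 16.8 − 12.8 = 4.0, SD (4.7 + 7.8)/2 = 6.25, two-sided 5%, 90% power. Per arm, n = 2 × (1.960 + 1.282)² × 6.25²/4.0² = 51.3. That is about 102.6 in total, or 104 after rounding up each arm, so 102 is reproduced closely. It does not address selection among 60 features. The current 40 comes from Section 5.7.

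**Nominal false-positive chance.** For k independent noise features tested at 0.05, the chance of at least one false positive is 1 − 0.95^k:

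- k = 3: 14%
- k = 4: 19%
- k = 60: 95%, with 60 × 0.05 = 3.0 false positives expected

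Cardiac segments are correlated, which lowers these figures, so stepwise selection was simulated.

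**Assumptions of the main simulation.** The documents give no event rate, feature correlation or selection level. Assumed: 40 patients with 12 cases (30%), one record each, logistic stepwise with entry and stay at p<0.05, at most 5 terms, equicorrelated normal features, 1000 datasets per setting, and new-data AUC from 2000 further patients. With 60 candidates and 12 cases there are 60/12 = 5 candidates per case. Optimism is apparent AUC minus new-data AUC.

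| Scenario (AUC of the one informative feature) | 60 features, correlation 0.3 / 0.6 / 0.8 | 4 features |
|---|---|---|
| All noise | 0.28 / 0.17 / 0.10 | 0.02–0.04 |
| Informative (0.75), others not shifted | 0.23 / 0.15 / 0.08 | 0.04–0.06 |
| Informative (0.85), others not shifted | 0.12 / 0.07 / 0.03 | 0.02–0.04 |
| Informative (0.75), others correlated proxies | 0.25 / 0.21 / 0.21 | 0.05–0.06 |
| Informative (0.85), others correlated proxies | 0.14 / 0.14 / 0.14 | 0.01–0.03 |

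All noise is a worst case. Section 1.5 defines subclinical cardiotoxicity partly by global longitudinal strain (GLS), which MyoStrain reports (Section 5.2), and partly by LVEF, so some signal is expected in both sets.

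**What is selected** (correlation 0.3 / 0.6 / 0.8):

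- All noise: at least one predictor kept in 79/48/27% of datasets from 60 features, against 16/10/8% from 4.
- Proxies, AUC 0.75: informative feature kept in 43/24/13%; at least one redundant feature kept in 85/83/88%.
- Proxies, AUC 0.85: informative feature kept in 82/51/23%; at least one redundant feature kept in 69/71/89%.

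**Sensitivity to the event count.** A separate all-noise simulation (400 runs per cell, at most 6 terms) used 8, 12 or 20 cases in 40 patients. From 60 features, at least one predictor was kept in 88–92%, 56–60% and 24–27% at correlations 0, 0.5 and 0.8, against 7–15% from 3 or 4 features. New-data AUC was 0.50 throughout.

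**Effect on the ranking.** In a further run of the proxy case at AUC 0.75, apparent AUC was 0.84–0.85 for 60 features against 0.73–0.74 for 4. On new patients it was 0.61–0.64 against 0.68. In that scenario same-data scoring reverses the order.

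**At 102 patients** (31 cases), 60-feature optimism is 0.20/0.14/0.08 for noise and 0.14/0.12/0.13 for proxies at AUC 0.75. The cut to 40 enlarges the problem but does not create it.

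**Repeated exams.** Pooling 40 × 6 = 240 exam rows, all noise, with within-patient correlation of 0.5 to 0.7 (assumed), gives apparent AUC of 0.66–0.79 for 60 features and 0.52–0.59 for 4. The independent units remain 40 patients.

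**The case against.** The strongest reply is that the plan has safeguards and that part (b) may have no target.

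- **Random forest.** Section 11 says it controls overfitting. It is named only for the partition trees. The likelihood-ratio test and information criteria apply to mixed models and are computed in-sample.
- **ROC and precision-recall comparison.** Section 11 compares areas under these curves for strain parameters and standard assessments. It does not say that they come from the stepwise models. If they describe single parameters, no selected model is scored by AUC. This stands, and it is why (b) stays conditional.
- **Figure 5.** Its caption refers to statistical methods, and the figure was not available. It could contain a validation step, so the absence is of stated text only.
- **Size.** With one strong feature (AUC 0.85), no proxies and correlation 0.8, optimism is 0.03 against 0.02–0.04, which is no material difference. One variant of the simulation even reversed the order in two no-proxy cells (0.036 versus 0.039 and 0.019 versus 0.035). A repeat with 250 datasets per cell found the 60-feature optimism larger in all 15 combinations of scenario and correlation. The no-proxy case is also artificial: unshifted correlated features act as suppressors, and at correlation 0.8 the best combination of 60 reaches AUC 0.93 or 0.99.
- **Pooled exams.** The plan names the MIXED procedure for repeated measures, so pooling exam rows is an assumption made here.

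None of this touches part (a).

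**Conclusion.** The concern holds. Followed as written, Section 11 yields a list of significant predictors whose p-values ignore the selection that produced them, at either sample size. If performance is also scored on the same data, optimism is 0.03 to 0.28 in AUC for 60 features and 0.01 to 0.06 for 4. These figures rest on the assumed event rate, correlations, signal and 0.05 selection level. The net direction of bias between the two sets in this trial is not established, because the true signal in each is unknown.

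This should be corrected but is not fatal. The fixed-cutoff sensitivity and specificity, the endpoint evaluation on discrete values and the 6-month segment comparison do not depend on the stepwise step.

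**What to change.** Add to Section 11:

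> The stepwise, tree and random forest models are exploratory. For both feature sets, performance is reported only from repeated stratified cross-validation, with all exams of a patient in one fold and variable selection repeated in each fold. P-values from selected models are not presented as evidence of significance.

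State also whether the two sets are fitted separately or pooled, which committee categories count as cases, how folds are stratified when a patient's status changes between exams, and how imputation is handled within folds.

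**Check of the wording.** With one record per patient (200 datasets per setting), cross-validated AUC was 0.50 for both sets in null data and 0.01–0.05 below new-data AUC in the proxy case. With six exams per patient (120 datasets, 60 features), patient-grouped folds gave 0.48–0.51 in null data, where the truth is 0.50. In the proxy case they gave 0.66–0.68, against 0.66–0.69 on new data. Folds that split a patient's exams gave 0.56–0.67 and 0.74–0.79, so the grouping clause is needed.

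**Cost.** Wording, and modest computing in the SAS, R and Python packages already named. Reported multi-feature performance will be lower. With one informative feature and no proxies, cross-validation reads 0.03–0.11 too low in both sets. Precision at 40 patients is poor: the SD of the cross-validated AUC difference between sets was 0.13–0.20 across simulated trials with signal, which is a further reason to call the comparison exploratory.

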1.3. Study Design

This is a prospective, multi-center, open label, randomized study. The study will enroll patients who exhibit subclinical myocardial dysfunction at baseline as determined by MyoStrain® evaluation.

Patients with any type of cancer scheduled to receive anti-cancer therapy, who are previously enrolled in the SURVIVE Registry, will be screened for study participation. Consented subjects meeting all inclusion/exclusion criteria will be enrolled into the PROACT study. Subjects will be randomized 1:1 between the MyoStrain® guided treatment arm and MyoStrain® observational arm. Patients in both randomized study arms will be followed with MyoStrain® testing at baseline, 1, 3, 6, 12, 24 & 36 month follow-ups, as outlined in the protocol.

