1.5. Endpoints

The primary efficacy endpoint is the sensitivity and accuracy of detection of patients with myocardial dysfunction using MyoStrain® compared to standard assessments of cardiac function: left ventricular ejection fraction (LVEF), as well as end-systolic (LVESV), end-diastolic (LVEDV), and stroke (LVSV) volumes indexed to body surface area.

Changes in function based on clinical presentation, standard assessments, and all available metrics will be used to define the cardiotoxicity status of the patient. A clinical committee organized and chaired by the principal investigator will be used to classify each exam in both unblinded and blinded arms according to professional knowledge and derived from the ASE Expert Consensus Position Paper, the ESC Position Paper, and the ESMO Clinical Practice Guidelines. [1] [2] [3]

- Clinical cardiac dysfunction is defined as an absolute change in LVEF > 10% from baseline to below 53% combined with heart failure symptoms or abnormal cardiac biomarkers (troponin, BNP, or NT pro BNP).
- Subclinical CTX was defined as an asymptomatic patient with a greater than 15% decrease in LVEF that remains >= 53%, worsening GLS more than 15% from baseline, or abnormal cardiac biomarkers (troponin, BNP, or NT pro BNP).
- If no baseline information is available to compare metrics for categorizing cardiotoxicity status, considering most patients in the PROACT sub-study of the Survive Registry will have metastatic cancer with prior treatments including chemotherapy, physician discretion and patient presentation will provide the final decision on cardiotoxicity category. All available metrics will be used to classify patients at each assessment time point.

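### Section 11 names no method for within-patient correlation of the per-exam cardiotoxicity status; if exams are pooled in the stepwise logistic model, stable null features are flagged in about 9% to 33% of analyses instead of 5%

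*Combined protocol and SAP*

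**What the plan says.** Four statements in the combined protocol and SAP bear on this point.

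- **Visits.** Section 1.3 has both arms "followed with MyoStrain® testing at baseline, 1, 3, 6, 12, 24 & 36 month follow-ups", which is seven exams per patient if none is missed.
- **Outcome.** Section 11 has a clinical committee decide among "no cardiotoxicity, functional decline without cardiotoxicity, subclinical cardiotoxicity, or clinical cardiac dysfunction at each exam timepoint". Section 1.5 agrees: "All available metrics will be used to classify patients at each assessment time point". The status is therefore a repeated four-level category.
- **Selection of predictors.** Section 11 uses multivariate and logistic regression with a stepwise "option to identify significant predictors at standard and guided care features for predicting cardiotoxicity". The candidates are more than 60 MyoStrain features and the standard measures LVEF, LVESV, LVEDV and stroke volume index.
- **Software.** "The regression will be implemented via GLM, LOGISTIC and MIXED (for statistical analysis of repeated measures) procedures in SAS". R's LMER is named as well, for graphics.

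The text names no generalized estimating equation (GEE), generalized linear mixed model, patient-clustered variance or conditional logistic model. It does not say whether the logistic model has one row per exam or one per patient, which visit is used if the latter, or how four categories enter the model.

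**The concern.** The plan recognises that its data are repeated measures, but it gives that role to a procedure that does not suit this outcome. GLM, MIXED and LMER are all linear models for a normal response. LOGISTIC is the only named regression procedure for a categorical response, and as named it has no patient effect and no within-patient correlation.

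If exam rows are pooled, several correlated rows from one patient are counted as separate pieces of evidence. Standard errors are then too small for any feature that, like the status, persists within a patient. Noise features of that kind pass the 5% level too often. Stepwise selection is how Section 11 identifies which features predict cardiotoxicity, and it feeds the comparison of MyoStrain with standard measures. With more than 60 MyoStrain candidates against four standard ones, excess false selections would fall mostly on the MyoStrain side.

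**Working it through.** **The plan's own figure.** The plan gives no error rate or correlation for this analysis. Section 11's one computed figure, 102 patients, concerns the 6-month segment count. With SD (4.7 + 7.8)/2 = 6.25 and difference 16.8 − 12.8 = 4.0, 2 × (1.96 + 1.2816)² × 6.25²/4.0² = 51.3, so 52 per arm or 104 in total, close to 102. It plays no part below.

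**Inputs.**
- From the documents: m = 7 exams (6 after baseline); 40 patients (Section 5.7) or 102 (Section 11).
- Assumed: within-patient status correlation ρ of 0.05, 0.2 and 0.5; a binary version of the status; a two-sided 5% test; pooled exam rows.

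**Step 1: feature constant within a patient.** Ignoring clustering understates the variance by the design effect DE = 1 + (m − 1)ρ. The true size of a nominal 5% test is 2 × [1 − Φ(1.96/√DE)].

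| ρ | DE, m = 7 | 1.96/√DE | True size |
|---|---|---|---|
| 0.05 | 1 + 6 × 0.05 = 1.3 | 1.72 | 8.6% |
| 0.2 | 1 + 6 × 0.2 = 2.2 | 1.32 | 18.6% |
| 0.5 | 1 + 6 × 0.5 = 4.0 | 0.98 | 32.7% |

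The number of patients does not enter the formula. With m = 6, at ρ = 0.05, 0.2 and 0.5, DE is 1.25, 2.0 and 3.5, and the size is 8.0%, 16.6% and 29.5%.

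**Step 2: feature that varies between exams.** If the feature's own within-patient correlation is r, then approximately DE = 1 + (m − 1)ρr. For m = 7 and r = 0.7, DE is 1.21, 1.84 and 3.1, and the size is 7.5%, 14.9% and 26.6%. At r = 0, DE = 1 and the size stays at 5%.

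**Step 3: simulation check.** Null feature, pooled rows, 6 exams, 25% of exams positive (assumed), 2,000 runs per setting, 40 patients.

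| Status correlation | Ordinary logistic, r = 1 | r = 0.7 | r = 0 | Patient-clustered SE, all r |
|---|---|---|---|---|
| 0 | 4.2% | 4.6% | 5.6% | 5.2–6.6% |
| 0.15 | 13.6% | 10.9% | 5.4% | 5.4–6.0% |
| 0.36 | 24.1% | 18.1% | 5.2% | 5.8–6.2% |
| 0.51 | 29.4% | 23.1% | 5.2% | 5.2–6.6% |

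For r = 1 the formula with m = 6 gives 13.8%, 24.2% and 29.8% at 0.15, 0.36 and 0.51, so the two agree. With 102 patients the r = 1 results are 13.2%, 22.9% and 29.9%. The problem therefore does not depend on which of the two sample sizes applies.

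**Step 4: one record per patient.** With m = 1, DE = 1 and there is no inflation from this source.

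**The case against.** The strongest reply is that no passage says exams are pooled. A reader might infer that the plan counts repeat exams as independent patients and that stable features will be falsely selected. The documents do not support that as fact. A logistic model on one status per patient (at 6 months, worst, or any event) also fits the text, and Section 11 does set 6 months as primary for the segment count. This stands, so the inflation must be stated conditionally. It does not dispose of the point. Status is assigned per exam, detection is to be compared over time, the Figure 5 caption covers every visit, and no patient-level status is defined. If one record was meant, the choice among up to seven statuses is still open.

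Further replies:

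- **Assumed inputs.** Every correlation and prevalence figure is assumed, and the check uses a binary outcome and single-feature tests. A reader might multiply the high-end rates by 60 features to get a count of false signals. That count is not supported: it would describe one-at-a-time screening of uniformly stable features, not the planned stepwise selection, which was not simulated.
- **Seven exams is an upper limit.** The LVEF and GLS criteria in Section 1.5 are changes from baseline, and visits may be skipped. Six exams lower the rates slightly (Step 1). Features analysed as change from baseline may lose part of the stability that drives the inflation.
- **Figure 5 is not reproduced.** It is captioned as showing statistical methods, so the gap can be confirmed only for the visible text.
- **Limits of the remedy.** GENMOD and GLIMMIX have no stepwise option either, and clustered errors do not cure stepwise selection among more than 60 candidates. Both are true, so the fix must treat selection separately.
- **Importance.** The stepwise regression is neither the primary endpoint of Section 1.5 nor the 6-month segment count. This limits the weight of the point.

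**Conclusion.** The point holds in conditional form. The visible text establishes that the status is a repeated four-level category, that its predictors are selected by stepwise logistic regression, and that no named procedure handles within-patient correlation for such an outcome. It leaves the row of the logistic model undefined.

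If exams are pooled, the more natural reading, a null feature constant within patients is flagged at the 5% level in about 9%, 19% or 33% of analyses with seven exams, at status correlations of 0.05, 0.2 or 0.5. The range rests on assumed correlations and on a binary version of the status. At the low end the excess is under four percentage points. It shrinks for features that vary between exams and vanishes for features with no within-patient stability or with one record per patient. The plan should be changed here, but nothing in this point affects the validity of MIXED for continuous outcomes.

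**What to change.** In Section 11, where the SAS procedures are named:

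1. State the row of each analysis of cardiotoxicity status, and how the four categories enter the model (ordinal or a stated binary split).
2. For analyses of per-exam status, replace LOGISTIC and MIXED with a patient-clustered categorical model: PROC GENMOD with REPEATED SUBJECT=patient and a small-sample-corrected sandwich variance, or PROC GLIMMIX with a random patient intercept and a visit term.
3. If stepwise LOGISTIC is kept, restrict it to one pre-specified record per patient, for example the 6-month status.
4. Keep MIXED for continuous outcomes such as strain, LVEF and segment counts.

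The cost is a few sentences and slightly more programming in the same package. The downside is wider standard errors and fewer predictors declared significant; with one record per patient, the stepwise model also uses less of the data. No extra patients, scans or visits are needed.
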